For each group, totally 3 section of therapy will be given in an interval of one week. The shock wave will be given by a two combined ESWT device from which 3000 impulses of shock waves with energy flux density of 1.5 bars and frequency of 5 Hz are delivered in the radial shock wave therapy group. For botulinum toxin group, botulinum toxin (dilution 500 U/2 mL in saline 0.9%) was administered. For the control group, a sham probe will be contacting the skin with the same therapeutic sound made. However, no energy will be delivered from the sham probe. The location of the applied therapy will be at biceps, flexor carpi radialis (FCR) and flexor carpi ulnaris (FCU) muscles.

Outcome measures:

The primary outcome of this study include, elbow and radio carpal joint range of motion (ROM), modified Ashworth scale (MAS), modified Tardieu scale (MTS), and Fugl-meyer assessment (FMA). The evaluation will be done before therapy sections, immediately, 1 month after, and 3 months after 3rd section of therapy. All examination will be done by the same examining physician who is blind to the allocation.

Modified Ashworth scale (MAS). The definition of the measured scales were as that proposed by Bohannon and Smith.³ Briefly, elbow joint range of motion will be performed manually. MAS is graded by the resistance felt during passive range of motion. However, for convenience in the statistical analysis, MAS 1+ was substituted by scale of 2, and 2, 3, and 4 were substituted by 3, 4, and 5, respectively.

Modified Tardieu scale (MTS). The definition of the measurement was as that proposed by Boyd and Graham (modified from Tardieu scale).^{4,5} In brief, the measurement of elbow and radio carpal range of motion will be performed at a slow and a fast velocity. The resulted joint angles at two speeds will be measured by goniometer. R1 angle is defined as angle of catch after a fast speed stretch and R2 angle is defined as angle measured during slow speed range of motion. The average of three testing will be used for analysis. The quality of muscle reaction during measurement will also be scaled.

Fugl-meyer assessment (FMA) The Fugl-Meyer assessment is designed to assess motor recovery following stroke. The maximum score of motor function of upper limbs were 66. It is a relatively simple assessment to administer and requires minimal training. The overall reliability for this instrument was high, as were the reliability measurements for the subsections of this assessment.

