Statistical analysis.

All statistic data will be analyzed by SPSS statistical software, version 20.0 (SPSS Inc., Chicago, USA). The homogeneity of patient demographic

characteristics in both comparative groups A and B were calculated with chi-square test for qualitative variables (gender, stroke subtype, affected site) and the ANOVA test for quantitative variables (age, weight, height, body mass index [BMI], time since onset of stroke). The differences between 3 groups were investigated using the repeated measures ANOVA followed by the Bonferroni post hoc tests. Statistical significance was set at $P<0.05$.

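### Four instruments share primary status with no success rule and no error control across them; if any one may succeed, the false-positive risk exceeds 5% on most readings, and four tests is a floor

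*Combined protocol and SAP*

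**What the plan says.** The Outcome measures section of the combined protocol and SAP opens: "The primary outcome of this study include, elbow and radio carpal joint range of motion (ROM), modified Ashworth scale (MAS), modified Tardieu scale (MTS"). The Fugl-Meyer assessment is the fourth instrument listed. No instrument is ranked above another. Assessments are at baseline and at three times after the third treatment session, and no visit is named as primary.

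The instruments contain several variables. Range of motion is named for two joints. The MAS paragraph refers to the elbow: "Briefly, elbow joint range of motion will be performed manually". For the MTS, "the measurement of elbow and radio carpal range of motion will be performed at a slow and a fast velocity". That gives an R1 angle and an R2 angle, where "R2 angle is defined as angle measured during slow speed range of motion". In addition, "The quality of muscle reaction during measurement will also be scaled".

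The Statistical analysis section gives one method: "The differences between 3 groups were investigated using the repeated measures ANOVA followed by the Bonferroni post hoc tests". It gives one threshold: "Statistical significance was set at" P<0.05. It contains no hierarchy of outcomes, no rule for combining them and no adjustment across them.

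The Design section is inconsistent on the number of arms. It states two groups of 21, then names three: shockwave (RSWT), botulinum toxin and control. The total is 42.

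**The concern.** A reader of this plan cannot tell which result would make the trial positive. With four co-equal primary instruments and no success rule, one significant instrument, a majority, or all four could each be presented as the planned criterion. The choice could be made after the results are known.

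The Bonferroni step does not close the gap. It adjusts comparisons between pairs of groups after the ANOVA for a given outcome; it does not adjust for analysing several outcomes. If success on any one is enough, the chance of at least one false positive grows with the number of outcomes tested, and the stated 5% no longer describes the trial's main claim.

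**Working it through.** **Plan's own figure.** The only error rate stated is P<0.05 per test. No effect size, standard deviation, power or dropout is given, so the sample size of 42 cannot be reproduced.

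**Inputs from the document.** Four instruments; threshold 0.05; repeated measures ANOVA followed by Bonferroni; 42 patients, either as two arms of 21 or, if split equally, three arms of 42/3 = 14.

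**Assumptions not in the document.** Normal data; one group-effect test per outcome; two-sided pairwise tests; a common correlation between outcomes of 0.9, 0.5 or 0; no true effect.

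**Step 1: how many variables.** The plan gives no count. Ours is:
- Low: ROM at 2 joints + elbow MAS + R1 at 2 joints + FMA = 2 + 1 + 2 + 1 = 6. This treats slow-speed R2 as the same angle as ROM and leaves out the quality score.
- High: add R2 at 2 joints and quality at 2 joints: 6 + 2 + 2 = 10.

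One test per instrument (four) is therefore a floor.

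**Step 2: independent outcomes, exact.** The chance of at least one false positive among k tests is 1 - 0.95^k.
- k = 4: 18.5%; k = 6: 26.5%; k = 10: 40.1%.
- One Bonferroni pair per outcome, at 0.05/3 = 0.0167: 1 - (1 - 0.0167)^4 = 6.5%.

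**Step 3: correlated outcomes, simulation** (40,000 null trials per cell). The ANOVA group effect is the one-way F test on each patient's mean over visits. Pairs use the pooled error with Bonferroni over three pairs, and count only if the F test is significant. Cells show the chance of at least one false positive, in percent, at correlation 0.9 / 0.5 / 0.

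| What counts as success | 4 tests | 6 variables | 10 variables |
|---|---|---|---|
| 3 x 14, omnibus F | 9.7 / 15.6 / 18.4 | 11.4 / 21.3 / 25.8 | 13.6 / 29.9 / 39.9 |
| 3 x 14, any Bonferroni pair | 8.3 / 13.4 / 15.6 | 9.8 / 18.2 / 22.2 | 11.8 / 26.1 / 34.5 |
| 3 x 14, either active arm v control | 6.1 / 9.8 / 11.5 | 7.3 / 13.8 / 16.2 | 8.9 / 19.8 / 26.1 |
| 3 x 14, RSWT v control only | 3.3 / 5.4 / 6.3 | 4.0 / 7.6 / 9.1 | 5.0 / 11.3 / 14.7 |
| 2 x 21, the single comparison | 9.4 / 15.7 / 18.7 | 10.9 / 21.0 / 26.5 | 12.9 / 29.2 / 40.1 |

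A separately written simulation agreed for four tests: three-arm omnibus 9.6 / 15.9 / 18.9, RSWT v control 3.4 / 5.6 / 6.4, two arms 9.5 / 15.6 / 18.6. With two arms there is only one pair, so Bonferroni removes nothing.

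**Step 4: the opposite rule.** If every instrument must succeed on one named test, the chance of all succeeding cannot exceed the chance that any given one does, so error is at most 5%. Simulated for four omnibus tests, 3 x 14, it is 1.7 / 0.1 / 0.0.

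**Step 5: after the fix.** With no true effect, Holm over four tests makes a false claim only if the smallest p-value passes 0.05/4 = 0.0125. Independent: 1 - 0.9875^4 = 4.9%. Simulated for the RSWT v control contrast: 2.5 / 4.3 / 4.9.

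**Step 6: power cost of Holm's first step.** Two-sample t-test, noncentral t, effect sizes assumed. The comparator is the level the plan already implies: 0.05 with two arms, 0.0167 with three.

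| Assumed difference | 2 x 21: 0.05 to 0.0125 | 3 x 14: 0.0167 to 0.0125 |
|---|---|---|
| 0.5 SD | 35% to 17% | 13% to 11% |
| 0.8 SD | 72% to 50% | 35% to 31% |
| 1.0 SD | 89% to 73% | 54% to 50% |
| 1.2 SD | 97% to 89% | 73% to 69% |

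**The case against.** The strongest reply is that the inflation is conditional. The plan never says that one significant instrument is enough, and if all four were required there would be no inflation. That stands. A reader might infer that the trial definitely runs at 8-19% error, but the document does not support this, because it states no success rule at all. The percentages show what one permitted reading costs; the firm defect is the missing rule.

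Second, the plan does contain a multiplicity step. It deserves credit for the group pairs: with three arms and only RSWT versus control counted, four tests stay near 5%. That relief depends on the count being four. At correlation 0.5 it is 7.6% for 6 variables and 11.3% for 10.

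Third, the count of 6 to 10 is ours. MAS at the wrist would make 11, and a single MTS index would give fewer. So neither four nor ten should be read as the plan's own number.

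Fourth, the low ends of the ranges need a correlation near 0.9, for which the document gives no evidence either way.

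Two further inferences are not supported. That the criterion could be chosen late is a risk left open by the text, not evidence of intent. And with three arms it would be wrong to price Holm as a fall from 72% to 50% power at 1 SD: that starts from an unadjusted 0.05, whereas the plan already tests pairs at 0.0167, so the fall is 54% to 50%.

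**Conclusion.** The concern holds in this form: the plan has four co-equal primary instruments, no rule for what makes the trial positive, and no control of error across outcomes. This follows from the text alone and applies under either reading of the number of arms.

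The size depends on an any-one-succeeds rule and the assumptions listed in the working. Four tests with three arms of 14 give about 10-19% on the omnibus test, 8-16% for any Bonferroni pair, 6-11% for either active arm versus control, and 3-6% for RSWT versus control only. Two arms of 21 give 9-19%. With 6 to 10 variables, the figures are about 10-40% for omnibus or any pair and 4-15% for RSWT versus control only. Separate visits and group-by-time effects are not counted; testing them as well would add further opportunities for a false positive.

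This should be corrected before analysis, because it determines what the trial can claim.

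**What to change.** Before any outcome data are analysed, adopt one of the following. The choice is the sponsor's.

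1. Name one primary variable, with one visit or one ANOVA effect and one group contrast, tested at two-sided 0.05. Label all other measures, visits, effects and contrasts secondary and supportive.
2. Keep the four instruments. For each, name one variable, one effect or visit, and one contrast, and apply Holm across the four at overall two-sided 0.05.

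Either way, the contrast can be named only once the two-group and three-group statements in the Design section are reconciled.

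The change is to protocol and SAP wording; it adds no patients or visits. Under (1) the other measures can no longer carry the main claim. Under (2) some power is lost, as tabulated in the working: 16 points at 1 SD with two arms of 21 (89% to 73%) and 4 points with three arms of 14 (54% to 50%). Those figures are the worst case, since Holm relaxes the threshold after each rejection.

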Design:

This study is a prospective and single blinded randomized control trial. The inclusion or the exclusion criteria will be assessed by the same physician before the patients are invited to join the trial. After the selected patients have signed the informed consent sheets, they will be randomized into two groups (21 patients in each group), the radial shockwave therapy group (RSWT group), the botulinum toxin injection group, and the control group. The randomization will be generated by a computer program and the allocation will be done with concealed envelops. Both the patients and the examining physicians are blind to the allocation. Treatment will be performed by another independent physician.

Participants:

Totally, 42 patients will be recruited from the department of Physical Medicine and Rehabilitation of the Taipei MacKay Memorial Hospital. Eligible subjects should meet the following inclusion criteria: (1) aged between 18 ~ 80 years old; (2) at least 6 months since onset of last stroke; (3) having at least 1+ in modified Ashworth Scale (MAS) score at the spastic elbow; (4) most important of all, read and signed the inform concern of this study.

The exclusion criteria are the following: (1) patients with elbow contracture (MAS=4); (2) patient who had prior history of botulinum toxin, phenol, alcohol injections, intrathecal baclofen pump or rhizotomy in six months; (3) having evidence of cognitive deficit; (4) having local infection, severe inflammation or otherwise lesion that is not suggestive for ESWT; (5) patient with serious medical problems, as uncontrolled hypertension,

coagulopathy, recent severe hemorrhage, neoplasm, severe hepatic disease, epilepsy, cutaneous pathology, mental retardation.

During the study period, physical therapy including range of motion (ROM) exercises, stretching, and others remained unchanged. Also, the doses of medication which might affect spasticity were not changed.

Interventions:

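### The plan names no decisive visit, model term or post hoc family, so a significant repeated measures ANOVA would not show whether any benefit lasts

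*Combined protocol and SAP*

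**What the plan says.** The Outcome measures section opens with a list of primary outcomes: "The primary outcome of this study include, elbow and radio carpal joint range of motion (ROM), modified Ashworth scale (MAS), modified Tardieu scale (MTS), and" the Fugl-Meyer assessment. It then gives the schedule: "The evaluation will be done before therapy sections, immediately, 1 month after, and 3 months after 3rd section of therapy". That makes one reading before therapy and three after it. No outcome is attached to a particular visit.

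The Statistical analysis section gives the comparison in one sentence: "The differences between 3 groups were investigated using the repeated measures ANOVA followed by the Bonferroni post hoc tests". The threshold follows ("Statistical significance was set at" P<0.05). Nothing says which term of the ANOVA decides the result, whether the post hoc tests compare groups overall or at each visit, or what counts as a positive trial.

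The number of arms is also unsettled. The Design section says "they will be randomized into two groups (21 patients in each group), the radial shockwave therapy group (RSWT group), the botulinum toxin injection group, and" a control group, which makes three named groups. The Participants section says "Totally, 42 patients will be recruited from the department of Physical Medicine and Rehabilitation".

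**The concern.** A schedule that runs to 3 months suggests interest in benefit that outlasts the sessions, although the plan does not say so. A response that is gone by 1 month and one that is still present at 3 months mean different things to a clinician, and the plan has no rule that separates them. The same data could be summarised by the group term, by the interaction, or by comparisons at single visits, and the choice could be made after the results are seen. This is separate from having several primary instruments. It would remain if only one were kept.

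**Working it through.** **The plan's own figures.** The documents give no power, effect size, SD or correlation, so no calculation can be reproduced. The only arithmetic available is 2 × 21 = 42. Three groups of 21 would need 63, and 42 over three groups is 14 each.

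**Assumptions (not from the documents).** One outcome with SD 1; equal correlation ρ = 0.4, 0.6 or 0.8 between visits; all four visits in the model (the natural reading, though not stated); two arms of n = 21; two-sided 0.05; effect d = 0.8 SD. The between-arm differences over the four visits are (0, 0.8, 0, 0) for an immediate-only effect and (0, 0.8, 0.8, 0.8) for a sustained one.

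**Reading 1: group-by-time decides.** The noncentrality is λ = (n/2) × S / (1 − ρ), where S is the sum of squared deviations of the differences from their mean, on 3 and 120 degrees of freedom.
- Immediate-only: mean 0.2, S = 0.6² + 3 × 0.2² = 0.48.
- Sustained: mean 0.6, S = 0.6² + 3 × 0.2² = 0.48.
- S is the same, so λ = 10.5 × 0.48 / (1 − ρ) = 8.4, 12.6, 25.2 for both patterns.

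**Reading 2: the group main effect decides.** The four visits are averaged. A sustained effect becomes (0 + d + d + d)/4 = 0.75d = 0.6, and an immediate-only effect becomes d/4 = 0.2. The noncentrality is λ = (n/2) × mean² / [(1 + 3ρ)/4], on 1 and 40 degrees of freedom.
- Sustained: 10.5 × 0.36 / (0.55, 0.70, 0.85) = 6.87, 5.40, 4.45.
- Immediate-only: 10.5 × 0.04 / (0.55, 0.70, 0.85) = 0.76, 0.60, 0.49.

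| Probability of a significant result, ρ = 0.4 / 0.6 / 0.8 | Immediate-only | Sustained |
|---|---|---|
| Group-by-time | 66 / 85 / 99% | 66 / 85 / 99% |
| Group main effect | 14 / 12 / 10% | 73 / 62 / 54% |

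**Three arms of 14.** With d = 1.0 in one arm and ρ = 0.5, the interaction has power 0.788 for either pattern. The group effect has 0.12 for immediate-only and 0.70 for sustained. The pattern does not depend on how the number of arms is resolved.

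**Unequal correlation.** With first-order autoregressive correlation of 0.6 and 0.8, simulation gave interaction rejection of 75% and 97% for the immediate-only effect, against 68% and 91% for the sustained one. The test's size was 6-7% there. Exact equality needs equal correlation, but the failure to favour a lasting effect does not.

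**Reading 3: visits tested singly.** With no true effect and no correction, the chance that at least one of three visits reaches 0.05 is about 13% at ρ = 0.4, falling to about 10% at ρ = 0.8. The figure under independence is 1 − 0.95³ = 14.3%. With 0.05/3 per visit it is below 5%.

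**One named visit.** An unadjusted comparison has noncentrality 0.8/√(2/21) = 2.59 on 40 degrees of freedom, and power 72%. Adjusting for the pre-therapy value divides the residual SD by 1/√(1 − ρ²), so the noncentrality becomes 2.83, 3.24, 4.32 and power about 79, 89, 99%. Simulation of the adjusted analysis is about one point lower at ρ = 0.4 and 0.6. These figures are for one contrast at 0.05. If three pairwise contrasts share the error rate (0.05/3 each), the same formula gives about 63, 77, 96%.

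**The case against.** The strongest reply is that the plan never mentions group-by-time. Its sentence is about differences between groups, so the group main effect is at least as plausible a deciding term, and under that term an immediate-only response would seldom be declared. This stands. A reader might infer that the planned test inherently treats a short-lived response like a lasting one. The documents do not support that, because it is true only if the interaction decides.

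A second reply is that Bonferroni is in the plan. If it covers group comparisons at each visit, it could locate the effect and hold the false-positive rate below 5%. This also stands as far as it goes. It would be wrong to infer that an uncorrected search over visits is planned, since the text only leaves the family undefined. But correction does not make any visit decisive: success at the immediate visit alone would still count as a positive primary result.

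A reader might also take the immediate reading for a pure same-day response. It follows three sessions a week apart and may reflect the earlier ones as well.

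Finally, a single-visit test might seem to waste data. Unadjusted, it does lose power against the interaction test at the higher correlations (72% against 85% and 99%). Baseline adjustment recovers this.

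**Conclusion.** The point holds in a conditional form. The plan leaves open which visit, which model term and which post hoc family decide, and under either ANOVA term a significant result does not show when the benefit occurred or whether it lasted. How often an immediate-only response would be declared positive runs from 10-14% (group term) to 66-99% (interaction), depending on a choice the plan does not make. The group term has its own cost: it reduces a sustained effect to 0.75d, with power of 54-73%.

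The percentages rest on an assumed effect of 0.8 SD, equal visit correlation and two arms of 21. That the deciding rule is missing rests on the text alone. The change is worth making because it settles what the trial can conclude and costs little.

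**What to change.** In Outcome measures, name one post-therapy decision visit before unblinding, and match it to the intended claim. A claim of benefit lasting 3 months needs the 3-month visit; the 1-month visit supports only a 1-month claim.

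In Statistical analysis:
- Make the between-group difference at that visit, adjusted for the pre-therapy value, the primary test for each outcome.
- Reconcile the two groups stated in Design with the three named there, then name the deciding pairwise contrast or contrasts and apply Bonferroni across them.
- Report the other visits as supporting estimates with confidence intervals, and keep the repeated measures model as a supporting analysis.

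This takes a few sentences and no extra visits or patients. The price is that a response seen only at another visit can no longer be the primary result. For a single contrast with 21 per arm, baseline adjustment keeps power at or about that of the interaction test (79, 89, 99% against 66, 85, 99%). If several contrasts share the error rate, power per contrast falls, which is a reason to keep the deciding contrasts few.

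### Every post-baseline visit is timed only from the third treatment session, so a randomised patient who stops before it has no scheduled outcome and would fall out of the analysis

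*Combined protocol and SAP*

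**What the plan says.** The Outcome measures section names range of motion, the modified Ashworth scale, the modified Tardieu scale and the Fugl-Meyer assessment as primary, and gives one schedule for all of them: "The evaluation will be done before therapy sections, immediately, 1 month after, and 3 months after 3rd section of therapy". Apart from baseline, no visit has any other reference point.

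The Interventions section sets the course of treatment for all arms together: "For each group, totally 3 section of therapy will be given in an interval of one week". Its sentence on the toxin arm gives a dilution only: "For botulinum toxin group, botulinum toxin (dilution 500 U/2 mL in saline 0.9%) was administered". It states neither a number of administrations nor how they relate to the three sessions. The control arm is described as "For the control group, a sham probe will be contacting the skin with the same therapeutic sound made".

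The Statistical analysis section says "The differences between 3 groups were investigated using the repeated measures ANOVA followed by the Bonferroni post hoc tests". The documents contain no visit window, no rule for a missed or postponed session, no assessment date for a patient without a third session, no analysis population and no method for missing data.

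**The concern.** Randomisation makes the arms comparable at the point of allocation. That comparability lasts only if everyone allocated is also measured. Here the right to a follow-up visit depends on reaching the third session, and whether a patient gets there can depend on tolerance, early response and willingness to attend. Those could plausibly differ between an injection, active shock wave and a sham probe.

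If they do differ, the patients who supply outcomes are no longer the randomised groups. The plan would have made this selection through its visit schedule, without anyone having chosen a completers' analysis. The loss is also permanent: an outcome that was never collected cannot be restored at analysis.

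A lesser issue comes from the same rule. If session 3 is postponed, every later visit moves with it, and no limit is stated.

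**Working it through.** **Inputs from the documents.** Three sessions one week apart in each group (Interventions). Visits at 0, 1 and 3 months after session 3 (Outcome measures). A total of 42, with 21 per group (Participants and Design). The plan gives no effect size, standard deviation, power or dropout rate, so its sample size cannot be rebuilt from a power calculation. The one figure that can be checked is 2 × 21 = 42, which agrees with the stated total. The Design section speaks of two groups but lists three. If three arms share 42, each has 42 / 3 = 14. Both arm sizes are carried below, because the documents do not settle which applies.

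**Step 1: the timetable as written.** Taking session 1 as day 0, session 3 falls on day 7 + 7 = 14. With 1 month taken as 30 days and 3 months as 91 days, the visits fall on days 14, 14 + 30 = 44 and 14 + 91 = 105. These days are the same in every arm, so the nominal timing difference between arms is 0 days.

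**Step 2: a patient who stops early.** Visit date = date of session 3 + offset. With no session 3, none of the three visits has a date. Only the baseline value is sure to exist. Standard repeated measures ANOVA uses patients with a value at every time point, and no other way of handling missing values is specified. Such a patient contributes nothing to the group comparison.

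**Step 3: weight of one patient.** 1 / 21 = 4.8% of an arm; 1 / 14 = 7.1%.

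**Step 4: illustration of scale (assumed range, not from the documents).** Suppose 5% to 20% of an arm does not reach session 3.

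| Arm size | 5% | 20% |
|---|---|---|
| 21 | 1.1 patients | 4.2 patients |
| 14 | 0.7 patients | 2.8 patients |

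**Step 5: illustration of bias (also assumed).** Let a share q of one arm be left out, and let those patients differ in mean outcome from those retained by D standard deviations. The full-arm mean is (1 − q) × retained mean + q × omitted mean, so the retained mean is off by q × D. If the comparison arm has no such selection, the contrast is off by the same amount.

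- q = 0.05, D = 0.5: 0.05 × 0.5 = 0.025 SD
- q = 0.20, D = 1.0: 0.20 × 1.0 = 0.20 SD

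If both arms lose the same share of similar patients, the two errors cancel. The bias arises from a difference between arms in who is lost.

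**The case against.** The strongest reply has four parts.

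**The plan does not say that non-completers go unassessed.** It sets visit times and defines no analysis population. This is true. But the only stated rule gives these patients no date, and the only stated analysis cannot use them. The silence leaves the problem in place.

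**Changing the reference point does not bring back someone who stops attending.** This stands: a patient who refuses visits is missing under any clock. It does not cover the patient who stops treatment but would still come for assessment, and that is the patient the present rule loses.

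**Timing from the end of a short, fixed course is a reasonable choice.** It asks what the effect is just after treatment and later. This stands too, and is a reason for caution about counting strictly from randomisation: a patient with a delayed session could have the first post-treatment assessment before treatment is finished. A visit window around the planned dates reduces this difficulty but does not remove it.

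**The size is not shown.** This stands. The documents give no non-completion rate, so it cannot be said that some patients will miss session 3, only that some may. Loss of power is not a useful substitute. For an assumed 1.2 SD difference at two-sided alpha 0.05 / 3, a loss of 2 of 14 per arm takes power from 73% to 64%, while a loss of 3 of 21 takes it from 91% to 85%. Both results depend on an effect size that the plan does not state, and neither measures selection.

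A reader might also infer that the toxin arm runs on a different clock, perhaps 14 days earlier, because toxin might be given only once. The documents do not support that. The Interventions section gives three sessions to each group. The offset needs two assumptions that appear nowhere: that there is a single administration, and that this arm's visits are counted from it.

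**Conclusion.** The concern holds in a limited form. All post-baseline assessments of the primary outcomes hang on an event after randomisation, and a patient who does not reach it has no scheduled outcome. With the analysis as specified, the result would describe treatment completers. This rests on the wording of the visit rule and on the standard form of repeated measures ANOVA; no assumed rate is needed.

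The size cannot be derived from the documents. What can be said is that each patient lost this way is 4.8% of an arm of 21, or 7.1% of an arm of 14. Under the assumed ranges in the working, the distortion of a contrast would be between 0.025 and 0.20 SD if the selection occurred in one arm only.

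No difference in assessment times between arms is shown. The toxin sentence is incomplete beside the three-session statement; that is a matter for the sponsor to reconcile and is not evidence of a timing bias.

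This is a worthwhile and cheap improvement to make before follow-up begins. It does not make the trial invalid.

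**What to change.** Add to the Outcome measures section that every randomised patient is assessed on the dates the present schedule already implies: the planned date of session 3 (about two weeks after session 1), then 1 and 3 months after that planned date. State a visit window, and state that the assessments take place whatever number of sessions was received.

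Add to the Statistical analysis section that each patient is analysed in the group to which they were randomised.

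Ask the sponsor to reconcile the toxin sentence in the Interventions section with the statement that each group has three sessions, so that the planned session dates are clear in all arms. No treatment rule is proposed here.

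The cost is a few sentences in the plan and a little extra effort to follow patients who stop treatment. The drawback is that a patient whose sessions slip beyond the window may be measured somewhat sooner after the last session than the present wording intends.

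### Does scoring the ordinal MAS as equally spaced integers, with only repeated measures ANOVA planned, call for a different primary analysis?

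*Combined protocol and SAP*

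**What the plan says.** The Outcome measures section lists MAS among the primary outcomes and describes it as a graded judgement: "MAS is graded by the resistance felt during passive range of motion". The same paragraph sets the scoring: "for convenience in the statistical analysis, MAS 1+ was substituted by scale of 2", and grades 2, 3 and 4 become 3, 4 and 5. Grades 0 and 1 are not mentioned and presumably keep their values, so the scores run from 0 to 5 in steps of one.

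Assessments are at baseline and then "immediately, 1 month after, and 3 months after 3rd section of therapy". The Statistical analysis section gives one method for comparing arms: "The differences between 3 groups were investigated using the repeated measures ANOVA", followed by Bonferroni post hoc tests at P<0.05. It does not name MAS, but no other method is offered. There is no rank test, ordinal model or alternative scoring.

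Under Participants, entry requires "having at least 1+ in modified Ashworth Scale (MAS) score at the spastic elbow" and excludes grade 4, so every patient starts at 1+, 2 or 3.

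**The concern.** ANOVA compares means, and a mean of ordered grades depends on the numbers attached to them. Convenience is the only reason given for these numbers. They make a move from 1+ to 1 worth the same as a move from 3 to 2, and nothing in the scale guarantees that. The recoded grades are also the ones patients occupy: 1+ is an eligible baseline grade, and patients who improve from 2 or 3 pass through it.

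If the spacing drove the result, the trial could report an MAS difference whose size comes partly from the scoring. A reader could not tell whether a borderline P value would survive an analysis using only the order of the grades.

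**Working it through.** The documents give no MAS standard deviation, effect size or power figure, so there is no planned number to reproduce. The check compares the plan's scores with an order-preserving alternative, 1+ = 1.5 with 2, 3 and 4 unchanged. That alternative is an assumption; the plan does not propose it. Both 14 and 21 per arm are used, because the Design and Participants sections give 42 patients and two groups of 21 but name three arms (42/3 = 14).

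**What the scores mean.** Under the plan every one-grade improvement counts 1, so a mean change is the average number of grades moved. Under the alternative, 2 to 1+ and 1+ to 1 count 0.5 each, while 3 to 2 counts 1.

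**Extreme constructed case, 21 per arm.** Five controls improve from 3 to 2, and 12 treated patients improve from 2 to 1+.
- Plan: 12/21 − 5/21 = 7/21 = 0.33, P = 0.028.
- Alternative: (12 × 0.5)/21 − 5/21 = 1/21 = 0.05, P = 0.67.
- Rank test on number of grades moved: P = 0.031.

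**Milder hypothetical case, 21 per arm, post-treatment grades.** Control: 6 at 1+, 9 at 2, 6 at 3. Treated: 4 at 1, 9 at 1+, 5 at 2, 3 at 3.
- Plan: difference 0.67, t = 2.467, P = 0.018. Standardised difference = t × √(2/21) = 2.467 × 0.309 = 0.76.
- Alternative: difference 0.40, t = 2.150, P = 0.038. Standardised difference = 2.150 × 0.309 = 0.66.
- Rank test (identical under either coding): P = 0.022.

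In both cases the order-only P value lies close to the plan's. The alternative coding is the outlier.

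**Simulation of the planned group-by-time ANOVA.** Three arms, four visits. Assumptions: latent severity N(1, SD 0.8), visit error SD 0.5, baseline limited to 1+, 2 and 3, three sets of grade cut-points, and a constant shift after treatment.
- Type I error with the plan's scores: 4.5–5.6% (3.9–5.2% with Greenhouse–Geisser correction). Repeat runs stayed within about 2–6%.
- The P<0.05 verdict differs between the two codings in 7.8–13.0% of trials when the largest shift is 0.6, in 0.6–4.9% at 0.9, and in 2.3–3.7% under the null.
- Active-minus-control improvement at shift 0.6: 0.73–0.82 points (plan) against 0.52–0.58 (alternative). These scales run 0–5 and 0–4. Standardised, the effects are 0.80–0.83 and 0.77–0.79.
- Power is 0.3–7.1 points higher with the plan's scores at shift 0.6.

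**The natural replacement: pairwise rank tests stratified by baseline grade, Bonferroni across three contrasts (0.05/3 = 0.0167).** Same model, asymptotic P values.
- At all three post-treatment visits there are 3 × 3 = 9 tests with no control across visits. The chance of any false positive is 9.7–12.0%, against 4.6–6.0% for the planned ANOVA.
- At one designated visit, power for any contrast is 34–47% with 14 per arm and 55–71% with 21, against 40–56% and 62–82% for the ANOVA. Comparing range ends, the loss is 40 − 34 = 6 to 56 − 47 = 9 points, and 62 − 55 = 7 to 82 − 71 = 11 points. Repeat runs vary by a few points either way.
- With 14 per arm, 59–90% of pairwise comparisons have a baseline-grade cell of two patients or fewer.

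**The case for a change.** The best argument for acting is that every factual element is correct. MAS is primary and ordinal, the spacing is justified only by convenience, and no ordinal check is planned. The raw mean difference is about 40% larger under the plan's scores than under the alternative (0.73/0.52 = 1.40; 0.82/0.58 = 1.41). About one trial in ten changes verdict at moderate power, which is plausible with 42 patients. An added procedure would use data already collected.

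Part of this stands. The raw MAS difference should be read as grades moved, not as a physical quantity, and the plan does not let a reader see whether a borderline P value is sensitive to the scores.

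The rest is weaker than it looks. Much of the 40% comes from the longer scale and nearly disappears on standardising. Verdict changes are also expected between any two reasonable tests: the stratified rank test and a change-score t-test on the plan's scores disagree in 9.9–14.6% of trials at shift 0.6. Disagreement with an assumed comparator therefore does not count against the plan. One of the three cut-point sets is equally spaced, so there the unit steps fit and the comparator does not.

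An odds ratio in place of the mean difference would bring its own assumption, proportional odds. Its likelihood-ratio test runs at 5.1–8.4% type I error with 14 per arm.

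**Conclusion.** The observation is accurate, but it calls for no change to the plan. Grade 1+ is not a number, so any analysis of means must code it. The plan's code is stated in advance, keeps the order and gives each grade step equal weight. The planned test stays near its nominal level, and its P values track the order-only ones in both worked examples. Choosing between this ANOVA and a sparse stratified rank analysis is a fair trade-off: the replacement loses roughly 6–11 points of power at one visit, or roughly doubles the chance of a false positive across three.

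Tabulating the original grades by arm and visit, or adding one ordinal sensitivity analysis at a single visit named beforehand, would help a reader with a borderline result. Either is optional and would correct no wrong number or bias.

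The simulated figures rest on the assumed latent model and cut-points, and the verdict-change rates also on the assumed 1+ = 1.5 comparator. The conclusion also takes the ANOVA to cover MAS, which the Statistical analysis section implies but does not state.
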